9.10 Other aspects

None.

10. Protection of human subjects

The study will be conducted in accordance with Good Epidemiology Practices⁹. This is a retrospective, non-interventional study and does not pose any risks for patients. All data used for the study will be de-identified with no breach of confidentiality with regards to personal identifiers or health information. Each database research partner will apply for an independent ethics committee review and/or other approvals according to local regulations.

Data protection and privacy regulations will be observed in collecting, forwarding, processing, and storing data from study subjects.

10.1 PHARMO Database Network - The Netherlands

The PHARMO Institute conducts research according to the latest directives regarding privacy and handling of data. The PHARMO Database Network combines data from different sources (pharmacy, hospital, laboratory etc.). Some of these databases are managed by PHARMO in-house and no permissions are required for access to data. For partnership databases, permissions are required for access to data. The various databases are probabilistically linked through validated algorithms that do not invade the privacy of the patients. Researchers only have access to data depleted of sensitive personal information (such as date of birth) that may be traced back to persons and study reports will contain aggregate data only. This approach is approved by the Dutch Data Protection Authority. Because of the use of de-identified data from existing databases without any direct enrolment of subjects, ethical approval or informed consent is not necessary according to the Dutch law regarding human medical scientific research (Wet medisch-wetenschappelijk onderzoek met mensen (WMO)), which is enforced by the Central Committee on Research involving Human Subjects (Centrale Commissie Mensgebonden Onderzoek, CCMO).

10.2 The Health Improvement Network (THIN) – United Kingdom

Centro Español de Investigación Farmacoepidemiológica (CEIFE) will comply with all applicable data protection, security and privacy laws, rules and regulations with respect to the collection, production, use, processing, storage, transfer, modification, deletion, and/or disclosure of any

information related to this study under this Agreement. CEIFE will ensure that information is not disclosed or transferred to any third party not mentioned in this protocol. CEIFE will ensure that appropriate technical and organizational measures are taken to protect information against accidental or unlawful destruction or accidental loss or alteration, or unauthorized disclosure or access and against all other unlawful forms of processing. CEIFE will store the Database used to perform this study at the premises of CEIFE. Privacy issues will be addressed and respected at each stage of the study. All analyses and reporting will be done on appropriately de-identified data and only in aggregate form. We will abide by the Guidelines for Good Pharmacoepidemiology Practices.⁹ The study protocol is dependent on approval by a Scientific Research Committee (SRC) for studies performed in THIN.

10.3 Health Search Database (HSD) - Italy

The Health Search institute (at Genomedics S.R.L.) has data from GPs, who registered clinical information on their patients during their daily clinical activity.

Given the use of encrypted data from an existing database without any direct enrolment of subjects, ethical approval or informed consent is not necessary according to the Italian law regarding human medical scientific research.

11. Management and reporting of adverse events/adverse reactions

As per the EMA Guideline on Good Pharmacovigilance Practices (Module VI–Management and reporting of adverse reactions to medicinal products), for non-interventional study designs that are based on secondary use of data, individual reporting of adverse reactions is not required. No expedited reporting of adverse events or reactions is required.

12. Plans for disseminating and communicating study results

Study protocol, study status, and report(s) will be included in regulatory communications in line with the risk management plan, Periodic Safety Update Report, and other regulatory milestones and requirements.

Study results will be published following guidelines of the International Committee of Medical Journal Editors¹⁰, and communication in appropriate scientific venues, e.g., International Society for Pharmacoepidemiology, will be considered.

When reporting results of this study, the appropriate STROBE checklist will be followed¹¹.

13. List of references

| | 2011/2012 starters N = n (%) | 2011/2012 starters N = n (%) | 2011/2012 starters N = n (%) |
| Age (years) | | | |
| <15 | | | |
| 15-<25 | | | |
| 25-<35 | | | |
| 35-<45 | | | |
| 45-<55 | | | |
| ≥55 | | | |
| mean ± SD | | | |
| median (IQR) | | | |
| Database history before index date (years) | | | |
| 1-<2 | | | |
| 2-4 | | | |
| >4 | | | |
| mean ± SD | | | |
| median (IQR) | | | |
| Follow-up after index date (months)* | | | |
| <6 | | | |
| 6-12 | | | |
| 13-24 | | n.a. | n.a. |
| mean ± SD | | | |
| median (IQR) | | | |

*by definition, the follow-up will not be longer than 24 months (start study period January 1, 2011, end study period December 31, 2012).

Table 14.2 General characteristics of new CPA/EE users in PHARMO, THIN and HSD in 2011, 2012 and 2014

| | PHARMO | | | THIN | | | HSD | | |
|---|-------------------------------|-------------------------------------|-------------------------------|-------------------------------------|-------------------------------------|-------------------------------|-------------------------------|-------------------------------------|-------------------------------|
| | 2011 starters N = n (%) | 2012 starters rs N = n (%) | 2014 starters N = n (%) | 2011 starters rs N = n (%) | 2012 starters rs N = n (%) | 2014 starters N = n (%) | 2011 starters N = n (%) | 2012 starters rs N = n (%) | 2014 starters N = n (%) |
| Age (years) | | | | | | | | | |
| <15 | | | | | | | | | |
| 15-<25 | | | | | | | | | |
| 25-<35 | | | | | | | | | |
| 35-<45 | | | | | | | | | |
| 45-<55 | | | | | | | | | |
| ≥55 | | | | | | | | | |
| mean ± SD | | | | | | | | | |
| median (IQR) | | | | | | | | | |
| Database history before index date (years) | | | | | | | | | |
| 1-<2 | | | | | | | | | |
| 2-4 | | | | | | | | | |
| >4 | | | | | | | | | |
| mean ± SD | | | | | | | | | |
| median (IQR) | | | | | | | | | |
| Follow-up after index date (months)* | | | | | | | | | |
| <6 | | | | | | | | | |
| 6-12 | | | | | | | | | |
| 13-24 | n.a. | n.a. | n.a. | n.a. | n.a. | n.a. | n.a. | n.a. | n.a. |
| mean ± SD | | | | | | | | | |
| median (IQR) | | | | | | | | | |

*by definition, the follow-up will not be longer than 12 months (end of study period is defined as December 31st of the year of the index date).

NOTE: in the interim report only data from the first run (2011/2012 users) will be available.

Table 14.3 Treatment characteristics of new CPA/EE users in PHARMO, THIN and HSD in 2011-2012

| | PHARMO | THIN | HSD |
|--|---|---|---|
| | 2011/2012 starters N = n (%) | 2011/2012 starters N = n (%) | 2011/2012 starters N = n (%) |
| Type of CPA/EE | | | |
| Diane 35 | | | |
| Generic | | | |
| Unknown | | | |
| CPA/EE prescriber | | | |
| GP | | n (100%) | n (100%) |
| Dermatologist | | n.a. | n.a. |
| Gynaecologist | | n.a. | n.a. |
| Other specialist | | n.a. | n.a. |
| Unknown | | n.a. | n.a. |
| Number of CPA/EE episodes during follow-up | | | |
| 1-2 | | | |
| 3-4 | | | |
| ≥5 | | | |
| mean ± SD | | | |
| median (IQR) | | | |
| Summed duration of CPA/EE use (months)* | | | |
| <6 | | | |
| 6-12 | | | |
| 13-24 | | n.a. | n.a. |
| mean ± SD | | | |
| median (IQR) | | | |
| Concomitant use of CPA/EE and HC**† | | | |
| Concomitant | | | |
| Potential concomitant | | | |
| Non-concomitant | | | |
| No use of HC | | | |
| Duration of concomitant use of CPA/EE and HC**† | | | |
| ≤28 days concomitant use | | | |
| >28 - 84 days concomitant use | | | |
| >84 days concomitant use | | | |
| mean ± SD | | | |
| median (IQR) | | | |
| Duration of potential concomitant use of CPA/EE and HC**† | | | |
| ≤28 days potential concomitant use | | | |
| >28 - 84 days potential concomitant use | | | |
| >84 days potential concomitant use | | | |
| mean ± SD | | | |

| | |
|--------------|--|
| median (IQR) | |
|--------------|--|

| |
|--|
| |
|--|

*follow-up is maximum 24 months; †users of CPA/EE may occur in multiple categories of concomitant use if more than one episode of HC is observed.

Table 14.4 Treatment characteristics of new CPA/EE users in PHARMO, THIN and HSD in 2011, 2012 and 2014

| | PHARMO | | | THIN | | | HSD | | |
|--|-------------------------------|-------------------------------|-------------------------------|-------------------------------|-------------------------------|-------------------------------|-------------------------------|-------------------------------|-------------------------------|
| | 2011 starters N = n (%) | 2012 starters N = n (%) | 2014 starters N = n (%) | 2011 starters N = n (%) | 2012 starters N = n (%) | 2014 starters N = n (%) | 2011 starters N = n (%) | 2012 starters N = n (%) | 2014 starters N = n (%) |
| Type of CPA/EE | | | | | | | | | |
| Diane 35 | | | | | | | | | |
| Generic | | | | | | | | | |
| Unknown | | | | | | | | | |
| CPA/EE prescriber | | | | | | | | | |
| GP | | | | n (100%) | n (100%) | n (100%) | n (100%) | n (100%) | n (100%) |
| Dermatologist | | | | n.a. | n.a. | n.a. | n.a. | n.a. | n.a. |
| Gynaecologist | | | | n.a. | n.a. | n.a. | n.a. | n.a. | n.a. |
| Other specialist | | | | n.a. | n.a. | n.a. | n.a. | n.a. | n.a. |
| Unknown | | | | n.a. | n.a. | n.a. | n.a. | n.a. | n.a. |
| Number of CPA/EE episodes during follow-up | | | | | | | | | |
| 1-2 | | | | | | | | | |
| 3-4 | | | | | | | | | |
| ≥5 | | | | | | | | | |
| mean ± SD | | | | | | | | | |
| median (IQR) | | | | | | | | | |
| Summed duration of CPA/EE use (months)* | | | | | | | | | |
| <6 | | | | | | | | | |
| 6-12 | | | | | | | | | |
| 13-24 | n.a. | n.a. | n.a. | n.a. | n.a. | n.a. | n.a. | n.a. | n.a. |
| mean ± SD | | | | | | | | | |
| median (IQR) | | | | | | | | | |
| Concomitant use of CPA/EE and HC**† | | | | | | | | | |
| Concomitant | | | | | | | | | |
| Potential concomitant | | | | | | | | | |
| Non-concomitant | | | | | | | | | |
| No use of HC | | | | | | | | | |
| mean ± SD | | | | | | | | | |
| median (IQR) | | | | | | | | | |
| Duration of concomitant use of CPA/EE and HC**† | | | | | | | | | |
| ≤28 days concomitant use | | | | | | | | | |
| >28 - 84 days concomitant use | | | | | | | | | |
| >84 days concomitant use | | | | | | | | | |
| Duration of potential concomitant use of CPA/EE and HC**† | | | | | | | | | |
| ≤28 days (potential) | | | | | | | | | |

| | | |
|---|--|--|
| concomitant use >28 - 84 days potential | | |
| concomitant use >84 days potential | | |
| concomitant use mean \pm SD | | |
| median (IQR) | | |

*follow-up is maximum 12 months; †users of CPA/EE may occur in multiple categories of concomitant use if more than one episode of HC is observed.

NOTE: in the interim report only data from the first run (2011/2012 users) will be available.

Table 14.5 Treatment of acne among new CPA/EE users in the year prior to index date in PHARMO, THIN and HSD in 2011-2012

| | PHARMO | THIN | HSD |
|---|---|---|---|
| | 2011/2012 starters N = n (%) | 2011/2012 starters N = n (%) | 2011/2012 starters N = n (%) |
| Users with acne diagnosis | N = n (%) | N = n (%) | N = n (%) |
| Topicals Topical antibiotics Corticosteroids in topical combinations Topical retinoids Other topical preparations Systemic preparations Systemic retinoids Systemic antibiotics Hormonal agents Hormonal contraceptives Antiandrogens | | | |
| Users without acne diagnosis | N = n (%) | N = n (%) | N = n (%) |
| Topicals Topical antibiotics Corticosteroids in topical combinations Topical retinoids Other topical preparations Systemic preparations Systemic retinoids Systemic antibiotics Hormonal agents Hormonal contraceptives Antiandrogens | | | |

Table 14.6 Treatment of acne among new CPA/EE users in the year prior to index date in PHARMO, THIN and HSD in 2011, 2012 and 2014

| | PHARMO | | | THIN | | | HSD | | |
|---|-----------------------------------|-----------------------------------|-----------------------------------|-----------------------------------|-----------------------------------|-----------------------------------|-------------------------------|-----------------------------------|-------------------------------|
| | 2011 starter s N = n (%) | 2012 starter s N = n (%) | 2014 starter s N = n (%) | 2011 starter s N = n (%) | 2012 starter s N = n (%) | 2014 starter s N = n (%) | 2011 starters N = n (%) | 2012 starter s N = n (%) | 2014 starters N = n (%) |
| Users with acne diagnosis | N = n (%) | N = n (%) | N = n (%) | N = n (%) | N = n (%) | N = n (%) | N = n (%) | N = n (%) | N = n (%) |
| Topicals Topical antibiotics Corticosteroids in topical combinations Topical retinoids Other topical preparations Systemic preparations Systemic retinoids Systemic antibiotics Hormonal agents Hormonal contraceptives Antiandrogens | | | | | | | | | |
| Users without acne diagnosis | N = n (%) | N = n (%) | N = n (%) | N = n (%) | N = n (%) | N = n (%) | N = n (%) | N = n (%) | N = n (%) |
| Topicals Topical antibiotics Corticosteroids in topical combinations Topical retinoids Other topical preparations Systemic preparations Systemic retinoids Systemic antibiotics Hormonal agents Hormonal contraceptives Antiandrogens | | | | | | | | | |

NOTE: in the interim report only data from the first run (2011/2012 users) will be available.

Table 14.7 Diagnoses of hyperandrogenic conditions among new CPA/EE users in the year prior to index date in PHARMO, THIN and HSD in 2011-2012

| | PHARMO | THIN | HSD |
|--|---|---|---|
| | 2011/2012 starters N = n (%) | 2011/2012 starters N = n (%) | 2011/2012 starters N = n (%) |
| Acne Alopecia Contraceptive management Hirsutism Menstrual problems Oligomenorrhoea/amenorrhoea Polycystic ovary syndrome Seborrhea | | | |

Table 14.8 Diagnoses of hyperandrogenic conditions among new CPA/EE users in the year prior to index date in PHARMO, THIN and HSD in 2011, 2012 and 2014

| | PHARMO | | | THIN | | | HSD | | |
|---|--|--------------------------------------|--|--------------------------------------|--|--|--------------------------------------|--|--------------------------------------|
| | 2011 starters rs N = n (%) | 2012 starters N = n (%) | 2014 starters rs N = n (%) | 2011 starters N = n (%) | 2012 starters rs N = n (%) | 2014 starters rs N = n (%) | 2011 starters N = n (%) | 2012 starters rs N = n (%) | 2014 starters N = n (%) |
| Acne Alopecia Contraceptive management Hirsutism Menstrual problems Oligomenorrhoea/amenorrhoea Polycystic ovary syndrome Seborrhoea | | | | | | | | | |

NOTE: in the interim report only data from the first run (2011/2012 users) will be available.

15. Annex 2. Additional information: figure and table shells for 2017 objectives

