Prior treatment of acne, according to European treatment guidelines², will be assessed in the year prior to the index date (index date – 365 days, excluding index date; for included product names and ATC codes see Table 16.3 and Table 16.4 in Annex 2). Acne treatments will be classified as topicals, systemic preparations and hormonal agents and assessed separately for patients with and without an acne diagnoses in the year prior to index date. Because many of the drugs in the tables are not specific for acne, a pragmatic approach will be taken to select actual acne treatment in the study population: 1) select drugs by ATC or Gemscript code; 2) define dose and route of administration; 3) check with local guidelines for the approved indication of use and only include drugs that are approved for acne (alternative indications may exist). This check with the local guidelines is efficient because only the drugs that are actually used in the study population have to be checked once this data is available. Acne treatments will be further classified to whether it is only approved for acne, or also approved for other indications to allow sensitivity analysis.

Prior diagnoses of hyperandrogenic conditions or medical conditions where EE/progestin combinations are prescribed for frequently will be assessed in the year prior to index date (index date – 365 days, excluding index date; for included codes, see Table 16.5 and Table 16.6):

- Acne
- Alopecia
- Contraceptive management
- Hirsutism
- Menstrual problems
- Oligomenorrhoea/amenorrhoea
- Polycystic ovary syndrome (PCOS)
- Seborrhoea

For the 2017 study extension the following will be assessed:

Demographic characteristics:

- Age at index date (in years, categorized, mean (\pm SD), median (IQR))
- History available prior to the index date (in years, categorized, mean (\pm SD), median (IQR))
- Follow-up available after the index date (in months, categorized, mean (\pm SD), median (IQR))

Concomitant use of hormonal contraceptives:

- Number of CPA/EE treatment episodes (categorized, mean (\pm SD), median (IQR))
- Summed duration of CPA/EE use (in months, categorized, mean (\pm SD), median (IQR))
- Concomitant use of hormonal contraceptives (concomitant, potential concomitant, non-concomitant or no use of hormonal contraceptives)
- Duration of concomitant use of CPA/EE and hormonal contraceptives (≤ 28 days concomitant use, $>28 - 84$ days concomitant use or >84 days concomitant use, mean (\pm SD), median (IQR))

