| 91324998 | Levonorgestrel 20micrograms/24hours intrauterine device |
| 91325998 | LEVONORGESTREL 52mg i-u system |

Table 16.3 ATC codes to identify treatment for acne in the year before index date in PHARMO and HSD

| Substance | ATC code* |
|---|------------------------------------|
| Topicals | |
| Topical antibiotics | D10AF |
| Corticosteroids in topical combinations | D10AA |
| Topical retinoids | D10AD |
| Other topical preparations | D10AB, D10AE, D10AX, D01AE12 |
| Systemic preparations | |
| Systemic retinoids | D10BA |
| Systemic antibiotics | J01AA08, J01AA07, J01AA02, J01FA01 |
| Other systemic preparations | D10BX |
| Hormonal agents | |
| Hormonal contraceptives | G03A |
| Anti-androgens | G03H |

NOTE: preliminary table, final codes will be selected based on local guidelines as described in section 9.3.

Table 16.4 Gemscript codes to identify treatment for acne in the year before index date in THIN

| Gemscript | Descriptor |
|-------------------|---|
| Topical solutions | |
| 74977994 | Generic aknicare lotion |
| 74979994 | Generic aknicare cream |
| 74985994 | Generic aknicare sr skin roller |
| 81780998 | Benzoyl peroxide 10% wash |
| 81783998 | Benzoyl peroxide 10% aq.gel |
| 81814998 | Benzoyl peroxide 5% gel |
| 82355998 | Benzoyl peroxide 10% gel |
| 82356998 | Benzoyl peroxide 5% gel |
| 82430998 | Adap 0.1% / ben perox 2.5% gel |
| 82431998 | Adapalene 0.1% / benzoyl peroxide 2.5% gel |
| 82939978 | Benzoyl perox+clind 3%/1% gel |
| 82940978 | Benzoyl peroxide 3% / clindamycin 1% gel |
| 82985998 | Nicotinamide 4% topical gel |
| 85337998 | Clindamycin 1% gel |
| 85550998 | Salicylic acid & sulphur cream |
| 85606998 | Azelaic acid 15% gel |
| 85608998 | Azelaic acid 15% gel |
| 86859998 | Nicotinamide 4% topical gel |
| 87171998 | Tretinoin with hydrocortisone and hydroquinone 0.1% + 1% + 5% cream |
| 87527998 | Benzoyl peroxide 5% / clindamycin 1% gel |
| 87865998 | Benz perox 5% / clindam 1% gel |
| 87866998 | Clindamycin 1% with benzoyl peroxide 5% gel |
| 88057996 | Chlorhexidine gluconate 1% solution |
| 88087998 | Erythromycin 4% topical gel |
| 88090998 | Erythromycin 2% topical gel |
| 88921998 | Benzoyl peroxide 10% lotion |
| 88923998 | Benzoyl peroxide 5% lotion |
| 89203998 | Nicotinamide 4% topical gel |
| 89241997 | Adapalene 0.1% cream |
| 89241998 | Adapalene 0.1% topical gel |
| 89242997 | Adapalene 0.1% cream |
| 89242998 | Adapalene 0.1% gel |
| 89561998 | Benz perox+pot hydrox sulf cream |

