| 99745998 | Azelaic acid 20% cream |
| 99784992 | Acne-aid soap |
| 99838992 | Aluminium comp paste pas |
| 99842992 | Aluminium oxide medium paste 52.2 % pas |
| 99843992 | Aluminium oxide fine paste 38.09 % pas |
| 99881998 | Aluminium oxide 38% paste |
| 99901998 | Benzoyl peroxide 10% lotion |
| 99902997 | Benzoyl peroxide 5% lotion |
| 99902998 | Benzoyl peroxide 5% cream |
| 99988998 | Generic actinac lotion |
| 99993998 | Benzoyl peroxide 5% gel |
| 99995998 | Benzoyl peroxide 2.5% gel |
| Systemic preparations | |
| 55596979 | Lymecycline 408mg capsules |
| 81719998 | Minocycline 100mg m/r capsules |
| 83064998 | Erythromycin 500mg tablets |
| 83065998 | Erythromycin stear 500mg tabs |
| 86390998 | Minocycline 100mg m/r capsules |
| 86753998 | Minocycline 100mg m/r capsules |
| 87959998 | Minocycline 100mg m/r capsules |
| 88431998 | Doxycycline 100mg capsules |
| 91308998 | Minocycline 100mg tablets |
| 91630998 | Doxycycline 100mg dispersible tablets sugar free |
| 92362998 | Doxycycline 100mg capsules |
| 92601997 | Minocycline 100mg tablets |
| 92601998 | Minocycline 50mg tablets |

| | |
|----------|--|
| 92775990 | Doxycycline 100mg capsules |
| 92854997 | Minocycline 100mg capsules |
| 92854998 | Minocycline 50mg capsules |
| 92856998 | Doxycycline 100mg capsules |
| 92931998 | Minocycline 50mg tablets |
| 93484992 | Doxycycline 100mg capsules |
| 93923998 | Doxycycline 100mg capsules |
| 94147979 | Erythromycin stear 500mg tabs |
| 94148979 | Erythromycin stear 500mg tabs |
| 94151979 | Erythromycin stear 500mg tabs |
| 94159979 | Erythromycin 500mg tablets |
| 94819997 | Erythromycin 500mg tablets |
| 94820996 | Erythromycin ethylsuccinate 500mg sachets |
| 94820997 | Erythromycin ethyl succinate 500mg tablets |
| 94848990 | Minocycline 100mg modified-release capsules |
| 94933998 | Lymecycline 408mg capsules |
| 95369992 | Oxytetracycline 500 mg tab |
| 95801997 | Minocycline 100mg tablets |
| 95801998 | Minocycline 50mg tablets |
| 95991998 | Lymecycline 408mg capsules |
| 96089990 | Doxycycline 100mg capsules |
| 96282990 | Doxycycline (as hyclate) 100mg tablets |
| 96305996 | Doxycycline (as hyclate) 100mg tablets |
| 96305997 | Doxycycline 100mg capsules |
| 96305998 | Doxycycline (as hyclate) 100mg dispersible tablets |
| 96354990 | Doxycycline 100mg capsules |
| 96781997 | Erythromycin stearate 500mg tablets |
| 96785997 | Erythromycin estolate 500mg tablets |
| 97051990 | Doxycycline 100mg capsules |

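### Tables 14.5 and 14.6 ask for systemic retinoids and anti-androgens in THIN, but no printed THIN code can find them, and the oral antibiotic lists differ between databases without explanation

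*Protocol*

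**What the plan says.** Section 8.1 of the protocol makes previous acne treatment one of the main objectives. Section 9.3 sorts acne treatment into topical, systemic and hormonal classes and describes three steps. The first is to "select drugs by ATC or Gemscript code". The second defines dose and route. The third keeps only products that local guidelines show as approved for acne.

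The shells in Annex 1 (Tables 14.5 and 14.6) print the same rows for all three databases, among them "Systemic retinoids Systemic antibiotics Hormonal agents Hormonal contraceptives Antiandrogens". No THIN cell in these tables is marked n.a.

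The codes are in Annex 3:

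- Table 16.3 (PHARMO and HSD) has "Systemic retinoids | D10BA", "Anti-androgens | G03H", G03A for hormonal contraceptives, and "J01AA08, J01AA07, J01AA02, J01FA01" for systemic antibiotics. Its footnote reads "preliminary table, final codes will be selected based on local guidelines as described in section 9.3".
- The THIN list is headed "Table 16.4 Gemscript codes to identify treatment for acne in the year before index date in THIN". It has one block of topical products and one of systemic products, and no hormonal block. It carries no footnote on preliminary status. Its systemic block includes entries such as "Lymecycline 408mg capsules".

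**The concern.** A shell row can be filled only if some code can find the drug. If a class has a row but no code in one database, the programmed result there is zero whatever the records hold. Next to PHARMO and HSD columns that do have codes, a reader would take that zero as a finding about UK practice.

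The antibiotic row raises a milder version of the same problem. It carries one label in three columns, but the lists behind it do not name the same number of substances.

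This bears on a main objective. Section 7 explains that CPA/EE is meant for acne only after other treatments have failed, so prior treatment is how the study describes whether that restriction is followed.

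**Working it through.** The plan states no figure to reproduce. The check sets the shell rows against the code lists.

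**Step 1. Rows against codes.**

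| Row in Tables 14.5/14.6 | PHARMO and HSD (Table 16.3) | THIN (Table 16.4) | THIN codes elsewhere |
|---|---|---|---|
| Systemic retinoids | D10BA | none | none |
| Systemic antibiotics | four ATC codes | 83 rows, five substances | not needed |
| Hormonal contraceptives | G03A | none | Table 16.2, but no pointer to it for this row |
| Antiandrogens | G03H | none | CPA/EE only (section 9.2) |

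Isotretinoin and tretinoin do appear in Table 16.4, but only as gels, creams, lotions and solutions in the topical block. The CPA/EE codes in section 9.2 do not fill the anti-androgen row, because use of CPA/EE in the prior year is an exclusion criterion in that section.

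**Step 2. Can the procedure in section 9.3 add a class?** Step 1 of that procedure selects on the listed codes. Steps 2 and 3 restrict what was selected. None of the three brings in a class that has no code, so the two THIN rows stay at zero.

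**Step 3. How many cells.** Each row appears twice per table, for women with and without an acne diagnosis. Table 14.5 has one THIN column: 2 rows × 2 blocks × 1 = 4 cells. Table 14.6 has three: 2 × 2 × 3 = 12 cells. In total, 4 + 12 = 16 cells are fixed in advance. The THIN calendar-year cohorts behind Table 14.6, as printed in Table 15.2, are 2,760, 2,923 and 2,341 women.

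**Step 4. How many women might be missed.** The documents give no prevalence for either class. As an assumption only, suppose 0.5%, 1%, 2% or 5% of the 5,600 THIN new users in section 9.5 had a GP-recorded prescription in a missing class:

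- 5,600 × 0.005 = 28
- 5,600 × 0.01 = 56
- 5,600 × 0.02 = 112
- 5,600 × 0.05 = 280

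If there was no such prescribing, the number is 0 and the printed zero happens to be right.

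**Step 5. Oral antibiotics.** Counting the systemic block of Table 16.4 by substance gives erythromycin 27, doxycycline 27, minocycline 24, lymecycline 4 and oxytetracycline 1, so 27 + 27 + 24 + 4 + 1 = 83 rows and five substances. Table 16.3 has four full-length ATC codes. Taking each as one entry, as Table 16.1 does for codes of that length, five substances cannot map one to one onto four codes. At least one substance therefore counts as acne treatment in THIN and has no printed code in PHARMO or HSD. The protocol does not say which substance each of the four codes denotes, so the comparison stops at the count.

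**The case against.** Several arguments on the other side have weight.

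- **THIN holds GP prescriptions only.** Section 9.9 says specialist prescriptions are not recorded in GP databases, so the missing codes may hide little or nothing. This stands as a limit on size. It does not explain the omission: HSD is also GP-only (section 9.6.3) and has both codes, and section 9.4.2 expects prescription acne treatment to be recorded by the GP in THIN without excepting any class.
- **The anti-androgen row may be nearly empty everywhere.** Prior-year CPA/EE is excluded in all three databases, and the approved-for-acne check may remove the rest. This also stands. An empty row after a search is still different from one that was never searched.
- **Local guidelines may justify different antibiotic lists, and the PHARMO/HSD codes are expressly preliminary.** This is a fair reading and may explain part of the difference. The protocol does not give it as the reason, and the row label does not warn the reader.
- **The treatments that section 7 names as having to fail first are topicals and antibiotics, which THIN does cover.** This is true, and it lowers the weight of the two empty rows.
- **The shells are blank, so n.a. might yet be printed.** That is possible. But the prescriber rows of Tables 14.3 and 14.4 already carry n.a. for THIN, and these rows do not.

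A reader might infer that the THIN zeros are known to be false, or that antibiotic use is understated by a definite amount in one database. The documents support neither. They contain no data on GP prescribing of these classes and none on the share of antibiotic users who take a substance found on only one list.

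**Conclusion.** The point holds in a limited form. Applied as printed, the THIN rows for systemic retinoids and anti-androgens are zero by construction and say nothing about use, so they cannot be compared with PHARMO or HSD. They understate use only to the extent that GP-recorded prescriptions exist. The 28 to 280 women shown above rest on an assumed 0.5% to 5%, not on any figure in the protocol. The antibiotic row may not measure the same drugs across databases; the five-against-four count shows that the printed lists differ, but not by how much the results would.

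The effect is confined to prior acne treatment in the 2011, 2012 and 2014 cohorts. The same two rows are empty in every year, so the damage is to comparison between databases rather than over time. The 2015–2017 extension does not assess acne treatment, and the concomitant-use results do not use these lists. It should be corrected, because the shells and the code lists disagree on a main objective and the remedy is cheap.

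**What to change.** - Add Gemscript codes for oral retinoids and for anti-androgens other than CPA/EE to Table 16.4. If these classes are deliberately not assessed in THIN, print n.a. in the THIN cells of Tables 14.5 and 14.6, as is already done for prescriber type, and say why.
- State that the THIN hormonal contraceptive row draws on Table 16.2, subject to the same approved-for-acne check as the other classes.
- Align the oral antibiotic substances between Tables 16.3 and 16.4, or add a footnote giving the local-guideline reason for each difference.
- State whether the preliminary-status note under Table 16.3 also applies to Table 16.4.

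The cost is a code-list edit and a re-run of the acne-treatment tables, with no new data source. Table 6.1 dates the final report on these cohorts to March 2016. If those tables are not to be reopened, n.a. entries and a footnote are the minimum.
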